1. When required in-person safety assessments (eg, clinical safety laboratory tests) can only be performed outside of a study visit window, the investigator should consider whether the safety of the trial participant can be assured with the delayed evaluation.
 - It is recommended that in-person safety assessments (eg, clinical safety laboratory tests) and efficacy assessments (eg, EGD) be performed no later than the timepoint that is halfway between two consecutive study visits.
2. When the subject cannot return to the study site or delegated study staff cannot be deployed to visit the subject for in-person safety assessments (eg, clinical safety laboratory tests) for submission to the central lab, the clinical safety laboratory tests may

be processed and analyzed by a local lab. This option will require prior agreement by the Sponsor.

3. Due to the risk of COVID-19 transmission from dispersion of respiratory droplets, medical societies or local/national public health officials may recommend that pulmonary function testing and DLCO be limited to tests that are essential for immediate treatment decisions.
 - When PFTs cannot be performed, the Sponsor may recommend other methods of monitoring respiratory health including measurement of arterial oxygen saturation (SpO₂) by pulse oximeter at Screening and post-baseline visits. It has been shown that the SpO₂ in patients with chronic obstructive pulmonary disease (COPD) correlates with the forced expiratory volume in 1 second (FEV₁) [70]. A pulse oximeter SpO₂ of $\leq 92\%$ on room air is 100% sensitivity and 86% specificity for detecting hypoxemia [71].
 - When Screening PFTs cannot be performed, Exclusion Criterion 18 may be modified as shown by the text in *italicized* font to identify and exclude subjects with underlying pulmonary disease at Screening: Have an FEV₁ or forced vital capacity (FVC) of $< 70\%$ predicted (prior to the administration of a short-acting bronchodilator) on Screening PFTs; *or a Screening pulse oximeter SpO₂ of $\leq 92\%$ on room air when Screening PFTs are not available due to COVID-19-related restrictions or a history of pulmonary disease requiring hospitalization ≤ 6 months prior to Baseline.*
 - Under the scenario above, the missed PFTs and DLCO must be performed no later than 10 days after COVID-19 restrictions are lifted and the PFT lab re-opens.

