APPENDIX 12: Liver Safety: Suggested Actions and Follow-Up Assessments

Potential Cases of Drug-Induced Liver Injury

Humans exposed to a drug who show no sign of liver injury (as determined by elevations in transaminases) are termed “tolerators,” while those who show transient liver injury but adapt are termed “adaptors.” In some subjects, transaminase elevations are a harbinger of a more serious potential outcome. These subjects fail to adapt and therefore are “susceptible” to progressive and serious liver injury, commonly referred to as DILI. Subjects who experience a transaminase elevation above $3 \times \text{ULN}$ should be monitored more frequently to determine if they are “adaptors” or are “susceptible.”

In the majority of DILI cases, elevations in AST and/or ALT precede T bili elevations ($>2 \times \text{ULN}$) by several days or weeks. The increase in T bili typically occurs while AST/ALT is/are still elevated above $3 \times \text{ULN}$ (ie, AST/ALT and T bili values will be elevated within the same laboratory sample). In rare instances, by the time T bili elevations are detected, AST/ALT values might have decreased. This occurrence is still regarded as a potential DILI. Therefore, abnormal elevations in either AST OR ALT in addition to T bili that meet the criteria outlined below are considered potential DILI (assessed per Hy’s law criteria) cases and should always be considered important medical events, even before all other possible causes of liver injury have been excluded.

The threshold of laboratory abnormalities for a potential DILI case depends on the subject’s individual baseline values and underlying conditions. Subjects who present with the following laboratory abnormalities should be evaluated further as potential DILI (Hy’s law) cases to definitively determine the etiology of the abnormal laboratory values:

- Subjects with AST/ALT and T bili baseline values within the normal range who subsequently present with AST OR ALT values $\geq 3 \times \text{ULN}$ AND a T bili value $\geq 2 \times \text{ULN}$ with no evidence of hemolysis and an alkaline phosphatase value $< 2 \times \text{ULN}$ or not available.
- For subjects with baseline AST **OR** ALT **OR** T bili values above the ULN, the following threshold values are used in the definition mentioned above, as needed, depending on which values are above the ULN at baseline:

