18.4. LABORATORY EVALUATIONS

No local laboratory assessments will be used in any summaries except for lipid panel and thyroid panel tests. No local laboratory assessments will be used to derive maximum/minimum/worst value. Local laboratory assessments will be listed.

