18.4.1. SAFETY LABORATORY EVALUATIONS

Hematology, serum chemistry, and coagulation are analyzed and reported by central laboratory and sometimes by local laboratory. Results out of reference range are flagged by the performing laboratory (e.g., low, high). A full list of laboratory assessments to be included in the outputs is included in Table 3 of protocol amendment v3.0 (04Jan2023).

Presentations will use SI Units. Quantitative laboratory measurements reported as “< X” or “> X”, where X may be the lower limit of quantification (LLQ) or the upper limit of quantification (ULQ), respectively, will be converted to X for the purpose of quantitative summaries, but will be presented as recorded, i.e. as “< X” or “> X” in the listings. For urinalysis, only pH and specific gravity are considered as quantitative tests. If local and central laboratory assessments are available from the same day, central laboratory assessments will be used in the summary as per Section 6.4.

The following summaries will be provided for laboratory data:

- Value and change from Baseline by visit (for hematology, TBNK panel, serum chemistry, quantitative urinalysis [pH and specific gravity], and coagulation)
- Incidence of abnormal values according to laboratory reference ranges by visit
- Incidence of lymphocytes $< 0.2 \times 10^9/L$, $0.5 \times 10^9/L$, or neutrophils $< 0.5 \times 10^9/L$, $1 \times 10^9/L$ at end of treatment and anytime in the study
- Change and Percent Change from Baseline in Absolute Lymphocyte Count (ALC) at Weeks 16, 24, 32, and 52
- Shift from Baseline to end of treatment according to laboratory reference range (for quantitative measurements and categorical measurements)
- eDISH plots for the following laboratory assessments:
 - Maximum Alkaline Phosphatase vs. Same-Day Total Bilirubin
 - Maximum Alkaline Phosphatase vs. Same-Day Total Bilirubin Adjusted for Elevated Baseline
 - Maximum Alanine Aminotransferase vs. Same-Day Total Bilirubin
 - Maximum Alanine Aminotransferase vs. Same-Day Total Bilirubin Adjusted for Elevated Baseline
 - Maximum Aspartate Aminotransferase vs. Same-Day Total Bilirubin
 - Maximum Aspartate Aminotransferase vs. Same-Day Total Bilirubin Adjusted for Elevated

Baseline

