If both central and local assessments of total bilirubin are available on the same day, the central result will take precedence over the local result in the eDISH plot. If the maximum AST/ALT/GGT assessment occurs at two different dates, the assessment with the higher accompanying Bilirubin value will be used. Two versions of the eDISH plots will be presented, with one showing values as multiples of upper limit of normal, and the other one showing values as multiples of upper limit of normal, or subject's baseline, whichever is higher.

Only laboratory tests completed by 50 or more subjects in the SAF will be presented in the summaries. All laboratory tests will be listed.

Subject's laboratory assessments at all timepoints will be listed in chronological order. Values outside of the laboratory reference range will be flagged. Values obtained from local laboratory will be flagged. Listing of lymphocytes and neutrophils over time in subjects ever with lymphocytes $<0.5 \times 10^9/L$ or neutrophils $< 1 \times 10^9/L$ will also be provided.

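### The eDISH plots pair peak ALT or AST only with that day's bilirubin, so a subject whose bilirubin rises after the transaminase peak can be plotted below the protocol's own threshold; the SAP's local-laboratory rules for these plots also conflict

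*SAP*

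**What the plan says.** **Pairing.** SAP 18.4.1 lists the plots "Maximum Alanine Aminotransferase vs. Same-Day Total Bilirubin" and "Maximum Aspartate Aminotransferase vs. Same-Day Total Bilirubin", each also in a version adjusted for elevated baseline. The only flexibility is for ties: "If the maximum AST/ALT/GGT assessment occurs at two different dates, the assessment with the higher accompanying Bilirubin value will be used".

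**Timing.** Protocol Appendix 12 states: "In the majority of DILI cases, elevations in AST and/or ALT precede T bili elevations", by several days or weeks. It adds that bilirubin typically rises while AST/ALT is still above 3 x ULN, so that both are raised in one sample. For rare instances it describes the other order of events: "by the time T bili elevations are detected, AST/ALT values might have decreased. This occurrence is still regarded as a potential DILI". Rises more than a few weeks apart are to be judged individually.

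**Criteria.** For subjects with normal baseline values, Appendix 12 flags a potential Hy's law case at AST or ALT >= 3 x ULN with total bilirubin >= 2 x ULN, no hemolysis, and alkaline phosphatase (ALP) < 2 x ULN or not available. Other thresholds apply when a baseline value is already raised.

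**Local results.** SAP 18.4 excludes local results from all summaries other than lipid and thyroid panels, and adds: "No local laboratory assessments will be used to derive maximum/minimum/worst value". SAP 18.4.1 lists the eDISH plots among the laboratory summaries, yet says of them: "If both central and local assessments of total bilirubin are available on the same day, the central result will take precedence over the local" result. Protocol Appendix 11 lets safety samples "be processed and analyzed by a local lab" in pandemic-type circumstances, with the sponsor's prior agreement.

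**The concern.** An eDISH plot is read by looking for points that are high on both axes. If bilirubin is taken only on the day of the transaminase peak, a subject whose bilirubin is still rising that day appears as an isolated transaminase elevation. Liver injury is an AESI in both documents, and choosing a dose on efficacy and safety is a primary objective. In the visible SAP text these plots are the only summary that sets transaminases against bilirubin: the AESI table counts transaminase and bilirubin elevations as separate subcategories, and the other laboratory summaries take one analyte at a time. With about 96 subjects planned, one misplaced point can change how the plot reads.

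The local-laboratory wording is a smaller, separate matter. Two programmers following different sentences could produce different plots from the same data.

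**Working it through.** No figure in the plan can be reproduced here. The check applies the SAP rule to constructed subjects (assumed values, multiples of ULN, normal baseline, ALP and hemolysis conditions met) and then sets the local-laboratory sentences side by side.

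**1. Bilirubin rising after the peak**

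| Sample | ALT | Bilirubin | ALT >= 3 and bilirubin >= 2? |
|---|---|---|---|
| 1 | 8 | 1.0 | No |
| 2 | 6 | 1.6 | No |
| 3 | 4 | 2.4 | Yes |

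- SAP rule: max(8, 6, 4) = 8 at sample 1, same-day bilirubin 1.0, so the point is (8, 1.0).
- The tie rule does not help, because the value 8 occurs once.
- Peak against peak: max(1.0, 1.6, 2.4) = 2.4, so the point is (8, 2.4).

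**2. The same on the visit schedule**

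Days 29, 57 and 113 are the Week 4, 8 and 16 visits. Days 64 and 71 stand for extra samples, since Appendix 12 asks for closer monitoring once transaminases exceed 3 x ULN.

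| Day | ALT | Bilirubin |
|---|---|---|
| 29 | 1.0 | 0.6 |
| 57 | 6.0 | 0.9 |
| 64 | 4.5 | 2.4 |
| 71 | 2.5 | 2.2 |
| 113 | 0.9 | 0.7 |

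- SAP rule: (6.0, 0.9). Day 64 meets both thresholds. Peak against peak: (6.0, 2.4).
- Without the day-64 sample, no single sample meets both thresholds: day 57 fails on bilirubin (0.9 < 2) and day 71 on ALT (2.5 < 3). This is the rare pattern that Appendix 12 still counts as potential DILI. Peak against peak gives (6.0, 2.2); a rule requiring one joint sample would miss it.

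**3. When the rule does no harm**

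If bilirubin is already >= 2 x ULN on the peak day, the subject is plotted correctly. The misplacement needs bilirubin to cross 2 x ULN after that day.

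**4. How often**

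This depends on the lag, the shape of the curves and the sampling interval. The documents give no lag distribution. Scheduled laboratory visits are mostly four or more weeks apart, with closer sampling only once an elevation is found. Under assumed curves the share misplaced runs from none (no lag) to nearly all (three-week lag, weekly samples), so no rate can be quoted for this trial.

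**5. Local results**

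- If SAP 18.4 governs, no local bilirubin enters the plot and the precedence sentence in 18.4.1 has nothing to do.
- If 18.4.1 governs, a local bilirubin is used when no central value exists that day, contrary to 18.4.
- The plots differ for a subject whose bilirubin on the peak day is local only: no bilirubin to plot in the first case, a plotted point in the second.

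A related slip: the tie rule names GGT, but the listed plots are for ALP, ALT and AST.

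**The case against.** The strongest reply is the protocol's own statement that bilirubin and transaminases are typically raised in the same sample. That is right, and it limits the problem, but the SAP does not plot any jointly raised sample. It plots only the one with the highest ALT or AST, and sample 3 in the first table is jointly raised without being the peak. Fallen transaminases are described as rare and should not be read as the usual course.

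It can also be said that the plot is not how cases are found. Appendix 12 has them evaluated at the site, preferably within 48 hours, and doubtful ones reviewed with the sponsor. SAP 18.2.6 has safety data, including serum transaminases, reviewed for AESIs that investigators missed. SAP 18.4.1 lists every laboratory value with out-of-range flags. The SAP also draws no quadrant; the thresholds used here come from Appendix 12. All of this stands. A reader might infer that the trial would overlook Hy's law cases, or would misplace most of them. The documents support neither: the safeguards do not depend on the plot, and no rate can be derived.

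Peak-against-peak plotting can join unrelated elevations months apart. That is a real cost and a reason to keep the same-day plots alongside.

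On local results, central processing is the default and the Appendix 11 route is narrow, so few subjects are likely to be affected. The sentences still cannot both apply.

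**Conclusion.** The point holds as a weakness of a summary display. Under the SAP's pairing rule, a subject who meets the Appendix 12 thresholds at a later sample can be plotted with a bilirubin from before the rise. The direction follows from the text alone; the size is unknown and rests on a lag that the documents do not describe. Nothing here shows that liver cases would go undetected. The conflict between SAP 18.4 and 18.4.1 is also real, narrow in reach, and a matter of reconciling wording. Both are worth correcting because the correction is cheap.

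**What to change.** 1. Add plots of maximum ALT and maximum AST against maximum total bilirubin over the treatment period through 30 days after last dose, or against the highest bilirubin in a pre-specified window after the transaminase peak. Keep the same-day plots as companions. State whether maxima are taken within each treatment period, so that a former placebo subject's two values do not come from different treatments.
2. Add a dated table of subjects meeting the Appendix 12 potential Hy's law criteria, with its baseline-adjusted thresholds and its ALP and hemolysis conditions. A bare count of ALT or AST >= 3 with bilirubin >= 2 x ULN would not match the protocol.
3. State one rule for local results. One option: local ALT, AST and bilirubin enter the threshold displays, as multiples of the performing laboratory's ULN, when no same-day central value exists, and by-visit summaries stay central only.
4. Align the analytes named in the tie rule with the plots listed.

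The cost is SAP wording, two added plots and one table, from data already collected. Some unrelated pairings will appear in the peak-against-peak plots; the dates in the table and case review resolve them.

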18.4.2. PREGNANCY TESTS

Urine beta-human chorionic gonadotropin (β -hCG) and/or serum β -hCG pregnancy tests are performed in female subjects of childbearing potential. All pregnancy test results will be listed in chronological order.

18.4.3. OTHER SCREENING LABORATORY ASSESSMENTS

Laboratory assessments for virology, T, B, NK, CD4+ T cell and CD8+ T cell counts (TBNK) and Urine drug screening will be listed. Analyses of genetics and **CCI** data based on samples collected in subjects who provided consent will be described in a separate plan.

18.5. ECG EVALUATIONS

ECGs are recorded on a 12-lead ECG machine and read locally and centrally. The following ECG parameters will be reported for this study:

HR (bpm)

PR Interval (ms)

RR Interval (ms)

QRS Interval (ms)

QT Interval (ms)

QTcF Interval (ms)

Overall interpretation of ECG (Investigator's judgment):

- Normal
- Abnormal, Not Clinically Significant (Abnormal NCS)

- Abnormal, Clinically Significant (Abnormal CS)

Overall interpretation of ECG (central reader):

- Normal
- Abnormal, Not Clinically Significant (Abnormal NCS)
- Abnormal, Clinically Significant (Abnormal CS)

The following summaries will be provided for ECG data:

- Value and change from Baseline by visit (for quantitative measurements)
- Incidence of markedly abnormal values (defined in Section 17.4.1) by visit
- Shift in normal/abnormal NCS/abnormal CS in the overall interpretation (by investigator) from Baseline to end of treatment and to the worst-case post-Baseline
- Shift in markedly abnormal categories from Baseline to post-Baseline by visit

All ECG results, including first dose cardiac monitoring, will be listed. Discharge criteria for first dose cardiac monitoring will also be listed.

A listing of all ECG assessments over time in subjects meeting markedly abnormal criteria will also be provided. For each subject, only ECG parameters ever meeting markedly abnormal criteria will be included.

18.5.1. ECG MARKEDLY ABNORMAL CRITERIA

Markedly abnormal quantitative ECG measurements will be identified in accordance with the following predefined markedly abnormal criteria:

- Absolute values in QT and QTcF:
 - ≥ 450 ms (male) or ≥ 470 msec (female) in QTcF
 - > 500 ms in QT
- Change from Baseline in QT and QTcF:
 - > 30 ms increase from Baseline
 - > 60 ms increase from Baseline

In shift tables, subjects will be classified according to the binary category for each parameter and the predefined markedly abnormal criterion (i.e., Markedly abnormal vs. Not markedly abnormal, with markedly abnormal defined in the footnote).

18.6. VITAL SIGNS

The following Vital Signs measurements will be reported for this study:

- Systolic Blood Pressure (mmHg)
- Diastolic Blood Pressure (mmHg)
- Heart Rate (bpm)
- Respiratory Rate (resp/min)
- Temperature (°C)
- Weight (kg)
- Height (cm) [Screening only]

The following summaries will be provided for vital signs data:

- Value and change from Baseline by visit
- Value and change from predose on Day 1 and Week 24 (as reported on the eCRF) by timepoint
 - For heart rate only, also include value and change from predose to minimum postdose heart rate on Day 1 in the same table
- Incidence of markedly abnormal values (defined in section 17.5.2) by visit
- Listing of subjects meeting markedly abnormal criteria
- Incidence of minimum heart rate on Day 1 by postdose timepoint (1, 2, 3, 4, and > 4 hours postdose, and Day 1 overall) and heart rate interval (≥ 65 , 60 to 64, 55 to 59, 50 to 54, 45 to 49, 40 to 44, < 40 bpm)
 - If minimum heart rate is attained at multiple postdose timepoints, only the earliest timepoint will be counted in this incidence summary
- Time to minimum heart rate on Day 1 by planned hourly timepoint (if minimum heart rate is attained at multiple postdose timepoints, only the earliest timepoint will be counted). Actual time elapsed from first dose to minimum heart rate on Day 1 will also be summarized using descriptive statistics (n, mean, SD, median, minimum, and maximum) in the same table.

All vital signs, including first dose cardiac monitoring, will be listed. Discharge criteria first dose cardiac monitoring will also be listed. A listing of all vital signs assessments over time in subjects meeting markedly abnormal criteria will also be provided. For each subject, only vital sign parameters ever meeting markedly abnormal criteria will be included.

For subjects with extended monitoring, systolic blood pressure, diastolic blood pressure and heart rate values and change from predose on Day 1 will be listed.

18.6.1. VITAL SIGNS SPECIFIC DERIVATIONS

- Temperature (°C) = (5/9) (Temperature (°F) – 32)

18.6.2. VITAL SIGNS MARKEDLY ABNORMAL CRITERIA

Markedly abnormal quantitative Vital Signs measurements will be identified in accordance with the following predefined markedly abnormal criteria:

Table 5: Markedly Abnormal Criteria for Vital Signs

Variable	Unit	Low	High
SBP	mmHg	≤ 90 mmHg	> 150 mmHg
DBP	mmHg	≤ 50 mmHg	> 90 mmHg
Heart rate	bpm	< 40 bpm < 50 bpm < 50 bpm and decrease from predose (Baseline) of > 10 bpm at 4 hours on Day 1 or remonitoring visit	>100 bpm

18.7. PHYSICAL EXAMINATION

A listing of all physical examination assessments in subjects who had at least 1 abnormal physical examination finding will be provided.

18.8. OTHER SAFETY ASSESSMENTS

18.8.1. PULMONARY FUNCTION TESTS

The following pulmonary function test (PFT) measurements (actual and % Predicted) will be reported for this study:

- Forced Expiratory Volume at 1 second (FEV1)
- Forced Vital Capacity (FVC)
- Total Lung Capacity (TLC)
- FEV1/FVC
- Forced Expiratory Flow (FEF) 25-75
- Diffusing Capacity of the Lungs for Carbon Monoxide (DLCO) (if available)

The following summaries will be provided for PFT data:

- Value and change from Baseline by visit
- Incidence of markedly abnormal values by visit

All PFT data will be listed. A listing in subjects who ever reported an abnormality in PFT will also be provided, including a flag for whether markedly abnormal criterion is also met.

